**Deleted:**

The visits and all research activities are outlined below:

Baseline Visit:

- Consent/Randomization
- Objective Measures:
  - o Serum collection
  - o Urine collection
  - o Synovial fluid collection
  - o General assessments
- Subjective Measures:

- o VAS Pain
- o KOOS-JR
- o UCLA Activity
- Intervention:
  - o Initial injection based on treatment arm

2 Weeks (+/- 6 days) Surveys:

- Subjective Measures:
  - o VAS Pain
  - o KOOS-JR
  - o UCLA Activity

4 Weeks (+/- 1 week) Follow-Up:

- Objective Measures:
  - o Serum collection
  - o Urine collection
  - o Synovial fluid collection
  - o General assessments
- Subjective Measures:
  - o VAS Pain
  - o KOOS-JR
  - o UCLA Activity

8 Weeks (+/- 13 days) Surveys:

- Subjective Measures:
  - o VAS Pain
  - o KOOS-JR
  - o UCLA Activity

12 Weeks (+/- 2 weeks) Surveys:

- Subjective Measures:
  - o VAS Pain
  - o KOOS-JR
  - o UCLA Activity

6 Months (+/- 2 month) Surveys:

- Subjective Measures:
  - o VAS Pain
  - o KOOS-JR
  - o UCLA Activity

**12 Months (+/- 2 month) Surveys:**

- Subjective Measures:
  - o VAS Pain
  - o KOOS-JR
  - o UCLA Activity

	Initial Visit	2 Weeks Surveys	4 Weeks Clinic Visit	8 Weeks Surveys	12 Weeks Surveys	6 Months Surveys	12 Months Surveys
Consent	X						
Randomization	X						
Serum Collection	X		X				
Urine Collection	X		X				
Synovial Fluid Collection	X		X				
General Assessments	X		X				
VAS Score (pain scale)	X	X	X	X	X	X	X
KOOS-JR	X	X	X	X	X	X	X
UCLA Activity	X	X	X	X	X	X	X
Injection	X						

**Surgical Specimen Collection:**

If it is indicated for a subject to undergo surgery (total knee arthroplasty), the meniscus and synovium that is normally resected and discarded after surgery will be collected for analysis. After collection, these tissues and data will be deidentified from the subject and assigned a number for use in study analysis. We seek to only collect tissues from subjects that are normally

removed and discarded during total knee arthroplasty procedures. None of the subjects will undergo additional surgical procedures for the collection of tissues in this study. Potential subjects must agree to the collection of these specimens to participate in the study, even if they do not end up needing surgical intervention.

### **VIII. Potential Risks:**

We do not expect any significant medical risks associated with the treatments presented in this study. Most of the risk associated with this study is related to piercing the skin by injection with synovial fluid collection and the venous blood draw. These can include the following: pain, bruising, bleeding, infection, and damage to surrounding structures, such as nerves and blood vessels. The risks of PRP injections include local infection and pain at injection site. The risks of corticosteroid injections include pain at injection site, skin discoloration, elevated blood sugar, infection, cartilage deterioration, and allergic reaction.

Synovial fluid collection in this study is part of the injection process and a stand-alone procedure at the 4-week visit. It has the same risk as the risk for injections listed previously. If there is a concern with the risks associated with the study, the participants are recommended to ask their provider for more information regarding the risks of the injection to their specific health condition. At any point, the participant has the right to withdraw from the study without recourse.

To help lower these possible risks, only professionally trained individuals will participate in the collection of the specimens. The participant will also be monitored for 5-10 minutes after injection.

All adverse events reported spontaneously by the participant or in response to questioning or observation by the investigator/research staff will be assessed for subject safety, acted upon as needed per situation and be recorded. If the events meet the criteria for IRB reporting, they will be reported to the IRB within five days.

Any adverse event associated with the intervention or deviation from the standard protocol will be evaluated related to subject safety and reporting requirements as well as any potential breach of confidentiality.

### **IX. Potential Benefits:**

Potential benefits include relief of their knee pain and return of function. Steroid injections have been shown to provide symptom relief for patients suffering from osteoarthritis. We also hope to demonstrate a differential efficacy between different corticosteroid and PRP injections, which would help guide future clinical decision-making.

## **X. Compensation:**

The subjects will not be compensated for their participation in the study.

## **XI. Costs:**

Most costs to run this study, including the cost of the injections, the equipment to draw blood and collect urine, the containers to store the blood until the tests are run, and the assays run in the laboratory, will be covered by the department. Participants will not incur any of these costs.

The subjects will be financially responsible for all their standard of care treatment. The initial visit is a standard of care, and the participant will be responsible for covering the cost of the visit itself, not the injection procedure or other testing that may occur during the visit. The 4-week visit is not standard of care and will be covered through an internal research fund. Any clinical visit scheduled due to a reoccurrence of knee pain is standard of care and the participant may choose to receive another injection if indicated. The participant is unblinded during this visit and may choose their preference of injection type if indicated. The participant will accrue the cost of the visit and for the injection if the participant chooses to receive the procedure.

All assays and tests will be completed in the laboratory of the same hospital where samples are acquired, so there will be no transportation outside of the hospital.

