## II. Drugs/Biologics/Devices

The biologic under investigation in this study is platelet-rich plasma (PRP), a concentrated solution of platelets of autologous origin. This product will be produced from approximately 15 milliliters of whole blood by a venous blood draw performed by a clinical medical staff within the patient exam room. This sample will be placed into a centrifuge located in the clinical office to collate the platelets within the sample for proper collection of PRP. The 15 milliliters of whole blood will produce approximately 4-6 milliliters of PRP. The volume of PRP administered will be approximately 4-6 milliliters via intraarticular injection in the affected knee of patients with moderate-to-severe knee OA. This amount of PRP is indicated because standard knee injections (a large joint injection) range from 5-10 milliliters of medical substance. The PRP will be administered during the initial visit.

The current standard of care for treatment of moderate-to-severe knee OA involves serial, intra-articular injection of a corticosteroid, with injections performed, at minimum, three months apart. This modality has been shown to provide short-term relief of knee OA symptoms, possibly by modulating the immune response and associated inflammatory cascade and will be used as the reference therapy in this study. However, a limitation of this treatment is a lack of understanding of its impact upon OA pathophysiology, and specifically cartilage degeneration. PRP has been

selected for this study because it has been shown to provide pain relief and increase functionality when administered as described. Moreover, its beneficial effect may persist longer than that of corticosteroid injection, as well as remove the potential for cartilage degradation associated with intraarticular corticosteroid treatment. A corticosteroid study arm is also implemented to compare standard of care treatment to the PRP treatment population.

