The medication used in the corticosteroid study arm is Triamcinolone Acetonide 40 mg/1 ml. The corticosteroid is to be ordered and regulated through the Investigational Pharmacy. The corticosteroid vials are to be stored in a lock box within the medical supplies room in the principal investigator's clinic. The medical supply room is up to IDS standards. Monthly temperature logs and expiration logs of the medication will be sent to IDS. The injection will consist of Triamcinolone 40 mg/1 mL (Kenalog) combined with 5 mL of 1% lidocaine and will be administered. The injection at the initial visit is the only established Triamcinolone injection within the study protocol. The participant may elect to receive an additional corticosteroid injection after 3 months after the initial injection if it is indicated by pain scores and physician clinical evaluation. This process may be repeated at other 3-month intervals within the study period, which is standard of care and an FDA approved use of the medication to control pain and treat the knee osteoarthritis.

An Investigational New Drug Application (IND) is not necessary for the products utilized in this study. We do not intend to report the investigation to the FDA as a well-controlled study in support of a new indication and with no intent to use it to support any other significant change in the labeling of PRP or triamcinolone. The use of these products does not involve a route of administration, dose, patient population, or other factors that significantly increases the risk associated with the use of the products. This investigation is not intended to promote or commercialize any of the products utilized.

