**Deleted: ¶**

Treatment Groups	First Injection
------------------	-----------------

Steroid Group	Triamcinolone 40 mg/1 mL (Kenalog) injection with 5 mL of 1% lidocaine
PRP Group	Platelet-rich plasma

*Blinding:*

Syringes will be prepared and masked with opaque tape by the clinic nurses, thus providing blinding for subjects.

A specimen of serum (from ~5mL of whole blood) and urine will be collected from the subject. If the subject's knee is aspirated prior to the injection (as commonly practiced), the synovial fluid will be collected, as well. These specimens will be deidentified and analyzed in the laboratory.

If the subject is randomized to the PRP group, the remainder of the PRP mixture not injected into the knee will be deidentified and analyzed in the laboratory.

Follow-Up/Clinic Visits:

Subjects will be required to complete VAS, KOOS-JR, and UCLA activity score surveys at baseline, 2 weeks, 4 weeks, 8 weeks, 12 weeks, 6 months, and 1 year. At the 4-week follow-up visit, urine and blood specimens will be collected as they were at the baseline visit. Synovial fluid collection will occur at this time point by a knee aspiration procedure.

Clinic follow-up evaluations will include a general assessment of appearance, range of motion, and function. ~~If the subject schedules another clinic visit within the one-year study timeline, subjects will be unblinded to which treatment arm they had received. At this visit or any time after, if an injection is indicated by participant pain and functionality scores, the participant has the choice to receive steroid or PRP injection, based on preference. If subjects in the PRP study arm experience severe pain, it is recommended to follow up with their physician for assessment and possible rescue therapy with corticosteroid injection. At any point during the study, the subject has the right to request rescue surgery and may proceed to do so with physician approval.~~

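### Section XI of the protocol allows elective PRP retreatment with no minimum interval, so a PRP injection on days 1-20 could precede the only post-treatment MCP-1 specimens (days 21-35)

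*Protocol*

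**What the plan says.** The retreatment permission stands in Section XI (Costs). It begins "Any clinical visit scheduled due to a reoccurrence of knee pain is standard of care" and goes on to say that "the participant may choose to receive another injection if indicated". The next sentence states that the participant is unblinded at that visit and "may choose their preference of injection type if indicated". No earliest date is attached.

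A similar permission in Section VII (Follow-Up/Clinic Visits), under which "the participant has the choice to receive steroid or PRP injection, based on preference", is struck through in the text at hand.

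The only intervals in the protocol concern corticosteroid. Section II describes the standard of care as serial corticosteroid "with injections performed, at minimum, three months apart". In the paragraph on the steroid arm it allows "an additional corticosteroid injection after 3 months after the initial injection if it is indicated by pain scores and physician clinical evaluation". For PRP, Section II says only that it is given at the initial visit.

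The primary objective is the effect of PRP on MCP-1 in serum, urine and synovial fluid. The schedule in Section VII collects these fluids at baseline and at one later visit, "4 Weeks (+/- 1 week) Follow-Up". It marks a study injection at the initial visit only.

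**The concern.** The post-treatment MCP-1 measurement is taken once, so anything injected into the knee between the randomised injection and that sample becomes part of what the sample measures. The protocol keeps repeat steroid well clear of the sample in the steroid arm, but sets no such limit on the product under study.

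Both arms are exposed:

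- **PRP arm.** A second PRP injection before sampling means that the week-4 value no longer reflects one injection. The secondary objectives themselves separate single from double PRP.
- **Steroid arm.** PRP before sampling means that the reference value no longer reflects steroid alone.

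This is a matter of trial conduct and cannot be left to the SAP. A SAP can say how to treat an affected value, but it cannot supply a specimen that was not taken before the injection.

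**Working it through.** The protocol states no figure on this point, so there is none to reproduce. The check is of timing, plus one proportion.

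**Inputs**

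- 4-week specimen visit: 4 weeks +/- 1 week (Section VII visit list).
- 2-week survey, which includes a pain score: "2 Weeks (+/- 6 days) Surveys" (Section VII visit list).
- Repeat corticosteroid: 3 months after the initial injection (Section II).
- Repeat PRP: no interval in any section.
- Planned arm size: 35, if funding allows (Section VI).

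**Step 1: windows, counting from the initial injection as day 0**

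- Specimens: 28 - 7 = 21 to 28 + 7 = 35, so days 21-35.
- 2-week survey: 14 - 6 = 8 to 14 + 6 = 20, so days 8-20. This lies wholly before the specimen window opens.

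**Step 2: which retreatment can precede the specimens**

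| Sequence | Interval stated | Can it precede days 21-35? |
|---|---|---|
| Steroid after steroid | 3 months, about 91 days | No: 91 - 35 = 56 days after the window closes |
| Steroid after PRP | Unclear; the Section II sentence sits in the steroid-arm paragraph but is worded generally | Depends on the reading |
| PRP after PRP | None | Yes |
| PRP after steroid | None | Yes |

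An injection on days 1-20 precedes any in-window specimen. On days 21-35 the order is open: specimens can be taken first at the same visit, but no section requires it.

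**Step 3: weight of one affected participant**

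1/35 = 0.0286, or 2.9% of that arm's week-4 serum and urine values, if the arm reaches 35 and all are sampled.

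**Step 4: the wait if elective PRP is deferred until sampling**

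Wait = S - d, with S the sampling day (21 to 35) and d the day of the pain visit.

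| d | S = 21 | S = 35 |
|---|---|---|
| 1 | 20 days | 34 days |
| 8 | 13 days | 27 days |
| 14 | 7 days | 21 days |
| 20 | 1 day | 15 days |

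The longest wait is 34 days, just under five weeks.

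**What cannot be computed.** The protocol gives no retreatment rate and no MCP-1 effect size or standard deviation. Section XIII says only that a power analysis was done. Any figure for lost power would rest on an assumed share of early retreatment, so none is given.

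**The case against.** The strongest reply is that this is a leftover and not a policy. Section XI explains who pays. The schedule marks one injection, Section II places PRP at the initial visit, and the matching paragraph in Section VII is struck through. On that view the remedy is to delete two sentences. This may well be right, and the fix puts it first. It does not remove the point, because Section XI as it stands still gives the permission and the protocol does not say which was meant.

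The second reply is rarity, and it largely stands. Early elective PRP needs relief, then recurrence, a scheduled visit, a clinical indication and payment by the participant, all within about three weeks. Section III also recruits patients who benefited from earlier injections.

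The third is that an extra injection would come to light. Section XII has staff review charts and ask at follow-up whether the participant has seen a doctor. That would probably reveal the injection, but it neither puts the specimens first nor marks an affected one.

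The fourth is that a broad retreatment rule could do harm. A 3-month steroid interval extended to the PRP arm would restrict care far beyond what the specimens need. Moving only symptomatic participants to day 21 would tie sampling time to symptoms. Both objections are sound, and the fix contains neither measure.

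A reader might infer from Section XI alone that either product may be repeated at any time. The protocol as a whole does not support that, since Section II limits repeat steroid in the steroid arm to three months. A reader might also infer that the primary comparison is materially distorted. With no frequency or effect size in the protocol, that does not follow.

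**Conclusion.** The point holds in a limited form. As written, the protocol lets elective PRP be given in either arm before the only post-treatment MCP-1 specimens, and no section sets an interval or an order of sampling to prevent it. The exposed period is days 1-20, together with days 21-35 when the injection is given before sampling.

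The size is unknown and probably small: 2.9% of an arm's week-4 serum and urine values per affected participant, at 35 per arm. The conclusion rests on reading Section XI as current text and the struck Section VII paragraph as withdrawn. Restoring that paragraph would not change it, because it sets no interval either. The point should be corrected because the measurement is primary, is taken once, and can be protected cheaply. Confidence is medium, mainly because the sentences may be a remnant.

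**What to change.** First decide whether choice of product at a pain visit is still intended.

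- **If it was withdrawn:** delete the retreatment-choice sentences from Section XI. Nothing further is needed on this point.
- **If it was kept:** put the rule in Section VII and let Section XI refer to it:
  1. Elective (non-rescue) PRP retreatment is not given until the 4-week specimens have been collected within the existing window.
  2. At any pain visit on days 21-35 where specimens are still outstanding, serum, urine and synovial fluid are taken before injecting.
  3. An earlier injection that the physician judges clinically necessary is not withheld. Its date and product are recorded, the 4-week specimens are still taken, and they are marked as post-retreatment.

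The steroid interval stays as Section II has it, and the 4-week visit window is unchanged for everyone.

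**Cost.** Protocol wording; two form fields (date and product); a line on who pays when a pain visit doubles as the 4-week visit; and a wait for elective PRP of at most 34 days. The rule also means that no elective second PRP can contribute to the week-4 comparison of single with double injections. Little is lost by that, since the schedule plans no second injection.

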## **VII. Study Procedures/Methods:**

### Enrollment/Randomization/Treatment Visit:

Eligible patients with primary osteoarthritis in at least one knee will be enrolled on a voluntary basis. Prior to the injection, patient-reported outcomes will be quantified using a visual-analog scale (VAS) to assess pain level, a Knee Injury and Osteoarthritis Outcome Score-Joint Replacement (KOOS-JR), and UCLA Activity score to assess functional activity level as part of standard care. These results will be deidentified and analyzed in the laboratory.

The patient will be randomized into one of two treatment arms. If the patient has a history of receiving bilateral knee injections for osteoarthritis and meets study requirements, randomization will occur for both knees. Randomization will be employed using a computer-generated random assignment sequence and results kept in concealed envelopes. The participant will be blinded to the injection regime received.

Enrolled patients will be randomized to one of two treatment arms:

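### Recurrent knee pain triggers unblinding and a choice of further injection with no earliest time, while self-scored outcomes run to 12 months and the sections describing this do not match

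*Protocol*

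**What the plan says.** Section VII (Enrollment/Randomization/Treatment Visit) promises participant blinding: "The participant will be blinded to the injection regime received". The means is given under Blinding in the same section: "Syringes will be prepared and masked with opaque tape by the clinic nurses, thus providing blinding for subjects". No other masking is described.

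Section XI (Costs) then limits how long that blinding lasts. It says "Any clinical visit scheduled due to a reoccurrence of knee pain is standard of care", allows another injection at that visit if indicated, and adds: "The participant is unblinded during this visit and may choose their preference of injection type if indicated". No minimum time since the initial injection is attached to the visit, the unblinding or the choice.

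Section II (Drugs/Biologics/Devices) covers further treatment differently: "The participant may elect to receive an additional corticosteroid injection after 3 months after the initial injection if it is indicated by pain scores", together with the physician's evaluation, and repeatable at later 3-month intervals. It mentions neither PRP nor unblinding.

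Section VII (Follow-Up/Clinic Visits) contains text on unblinding and choice of product, but that text appears struck through, among marks of tracked deletions.

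On outcomes, section VII says: "Subjects will be required to complete VAS, KOOS-JR, and UCLA activity score surveys at baseline", and the schedule continues at 2, 4, 8 and 12 weeks, 6 months and 1 year. Blood, urine and synovial fluid are scheduled at baseline and 4 weeks.

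On the injection visit, everyone gives a research sample: "A specimen of serum (from ~5mL of whole blood) and urine will be collected from the subject". For PRP, section II describes in addition production from "approximately 15 milliliters of whole blood by a venous blood draw performed by a clinical medical staff within the patient exam room", followed by a centrifuge step in the clinical office.

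**The concern.** All three surveys are scored by the participant, and one of them measures pain. Pain also prompts the visit at which allocation is disclosed. Unblinding is therefore related to the outcome: participants doing badly are the ones told their arm, and each later score comes from someone who knows the arm and may have chosen a second product. If one arm controls pain less well, unblinding and re-injection will be more frequent there, and later comparisons will mix the randomised treatment, knowledge of it, and the further injection.

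At stake are the secondary objective on patient-reported outcomes and the hope, in section IX (Potential Benefits), of showing a difference in efficacy between the products. An analysis plan may choose how to handle scores after unblinding or re-injection, but only if the dates exist. The protocol does not ask for surveys before disclosure, for the unblinding date, or for the date and product of a further injection. Data not captured cannot be recovered later.

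The mismatch between sections adds a practical problem: site staff have no single rule to apply, so the timing of disclosure may vary between participants.

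**Working it through.** **1. The sections side by side**

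| Point | Section XI (Costs) | Section II (Drugs) | Section VII (appears struck through) |
|---|---|---|---|
| Trigger | Visit for recurrent knee pain | Pain scores and physician evaluation | Any further clinic visit within the year; injection on pain and function scores |
| Unblinding | Yes, at that visit | Not mentioned | Yes, at that visit |
| Earliest time | None stated | 3 months after the initial injection | None stated |
| Product | Participant's preference | Corticosteroid only is mentioned | Steroid or PRP, by preference |

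If the struck text is withdrawn, the only live unblinding rule sits in the Costs section. If it stands, it agrees with section XI on disclosure and choice, but its trigger is wider.

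**2. Surveys that follow a pain visit**

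Inputs: seven survey times (section VII and the schedule table), of which one is baseline, so 7 − 1 = 6 are post-baseline. If k of these are complete when the visit occurs, 6 − k remain. At nominal times:

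| Pain visit falls | k | Surveys after it |
|---|---|---|
| Before week 2 | 0 | 6 |
| Weeks 2 to 4 | 1 | 5 |
| Weeks 4 to 8 | 2 | 4 |
| Weeks 8 to 12 | 3 | 3 |
| Week 12 to month 6 | 4 | 2 |
| Months 6 to 12 | 5 | 1 |

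The visit windows could shift these counts for an individual. For comparison, suppose the 3-month interval in section II also governed unblinding, which it does not say. Three months is about 52/4 = 13 weeks, after the nominal 12-week survey, so 2 or 1 surveys would follow (3 if the 12-week survey were done at the end of its 2-week window, at week 14). How the sections are reconciled therefore decides whether the early surveys are exposed.

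**3. The 4-week sample**

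The only post-baseline fluid samples are at 4 weeks (± 1 week). Section XI does not exclude a pain visit before then. Such a visit would precede the sample, and so would any further injection given at it.

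**4. Possible cue at the injection visit**

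- Blood drawn: about 5 mL from everyone. For PRP it is about 15 mL in total if the serum sample comes out of the production draw, or 15 + 5 = 20 mL if it is additional; the protocol does not say which. The difference between arms is 15 − 5 = 10 mL to 20 − 5 = 15 mL.
- Injected volume: steroid 1 + 5 = 6 mL; PRP 4 to 6 mL. The difference is 0 to 2 mL and the volumes overlap.
- Preparation: centrifugation is described for PRP only, with no matching step or wait in the steroid arm.

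Both arms have a venous draw, so having blood taken is not the cue. The possible cues are the larger volume, the processing and any wait. These figures describe a cue; they do not measure unblinding.

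**The case against.** The strongest reply is that section XI describes deliberate, disclosed unblinding at a standard-of-care visit. It limits the duration of blinding and is not a failure of masking, and the analysis of later scores belongs to the analysis plan, which is not at hand. This stands as far as analysis goes. It does not cover the missing records.

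A reader might infer that sections II and XI flatly contradict each other. The documents do not support that. The section II text stands in a paragraph on the corticosteroid product, so its silence on PRP and unblinding does not exclude either. Section XI allows a further injection only if indicated, so for corticosteroid the two can be read together. What stays open is the timing of the visit, of unblinding and of a further PRP injection. That is a mismatch to reconcile. The status of the struck text may also be clearer in the source file than in the text available here.

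A reader might also infer that blinding fails at baseline. That is not shown. All participants have blood taken, the injected volumes overlap, the syringes are taped, and the centrifuge is placed in the clinical office, which is compatible with processing out of view. In bilateral participants both knees are randomised; if the knees can differ in arm (not stated), the draw would not show which knee received PRP. This part is a risk only.

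Finally, recording surveys before disclosure protects that one assessment and none after it, and a second injection alters later scores even in a blinded participant. Both points are right, which is why the dates and the product are needed as well.

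**Conclusion.** The concern holds in this form: live protocol text unblinds on recurrent pain, with no earliest time and a choice of product, while self-scored outcomes continue to 12 months, and the three places that bear on it do not match. From 1 to 6 of six post-baseline surveys would follow such a visit, for a visit before the 12-month survey and at nominal survey times. The number of participants affected and the direction and size of any bias cannot be obtained from the protocol.

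It would go too far to say that the primary MCP-1 result is compromised. MCP-1 is a laboratory measurement on deidentified specimens, and knowledge of the arm should affect it little. The exposure is narrower: a further injection before the 4-week sample, which section XI does not rule out.

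The baseline cue is a lesser point. It rests on the protocol not saying whether the draw and preparation can be seen or are matched. Overall this should be corrected; it does not undermine the trial as a whole.

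**What to change.** 1. At any visit for recurrent pain, have the participant complete VAS, KOOS-JR and UCLA before allocation is revealed.
2. Log the date of unblinding, and the date and product of any further injection, so that blinded scores from before any further injection can be separated from later ones.
3. Reconcile sections II, VII and XI on whether and when unblinding and further injections apply, state whether the struck-through text in section VII is withdrawn, and put the resulting rule in the procedures section. The content of that rule is a clinical matter for the investigators.
4. As a lesser step, keep the drawn volume and the PRP preparation out of the participant's view, with a similar wait in both arms.

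The cost is protocol wording, one extra set of three surveys per pain visit, two dates and a product field in the case report form, and some added waiting in the steroid arm. The length of that wait cannot be stated because the protocol gives no preparation time. No extra blood, visits or participants are needed.
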